6.2.1.2.4 Determination of Adverse Event Severity and Relatedness

Determination of the severity of adverse events will be consistent with CTCAE, version 4.0. The relationship of an adverse event to investigational product will be determined by the investigator. An adverse event will be considered related to study treatment (possibly, probably, or definitely related to the study treatment) if there is a suspected “reasonable causal relationship” to the study treatment (ICH E2A), and not only a lack of an alternative explanation for the toxicity (*NCI Guidelines for Investigators - Adverse Event Reporting Requirements*, Sept, 2013) (see [Section 9](#) – Safety Data Collection, Recording, and Reporting).

6.2.1.2.5 Cohort Dose Level Determination

Study Part 1

A Dose Level Review Team (DLRT) will convene before a decision is made to open study Part 2. At the start of Part 1, enrollment of the first cohort of 6 to 9 evaluable patients will open for enrollment with a starting dose of AMG 820 1400 mg plus pembrolizumab 200 mg Q3W. Following subject completion of the DLT period, the DLRT will review all available safety data for the first cohort. If the data supports continued dosing at the selected starting dose, study Part 2 will be initiated at the same dose level. If it is determined that the starting dose is non-tolerable (if 33% or more of the evaluable subjects experience a DLT), dose de-escalation will occur and a second Part 1 cohort will be enrolled to test a decreased dose of AMG 820 in combination with 200 mg pembrolizumab Q3W. This will occur until identification of a well-tolerated dose for study Part 2. The AMG 820 (mg) pre-specified nominal cohort dose levels to be explored are 1100 mg and 800 mg Q3W. The pembrolizumab dose level will remain at 200 mg Q3W.

Part 2

Part 2 will have 4 groups, which will be evaluated using a Simon two-stage design:

Table 1. Study Part 2 Subject Groups

Naïve to anti-PD-1/PD-L1/CSF-1/CSF-1R treatment	
Group 1	CRC ^{MMR-proficient}
Group 2	Pancreatic Cancer
Group 3	NSCLC ^{PD-L1 low}
Refractory/ relapsing on anti-PD-1/PD-L1 + naïve to CSF-1/CSF-1R treatment	
Group 4a	NSCLC ^{PD-L1 low}
Group 4b	NSCLC ^{PD-L1 high}

The dose or doses (proposed recommended phase 2 dose, RP2D) to be evaluated in part 2 of the study will be based on results from part 1. The DLRT may determine the RP2D, which is defined as a dose(s) that is/are safe and produces pharmacodynamic effects. Emerging safety data may be used to re-challenge the selected dose in Study Part 1. If the initially selected dose is re-challenged, additional subjects may be enrolled in the corresponding cohort. In addition, the study may be discontinued or modified at any time due to documented safety findings.

Enrollment into the second stage of the Simon two-stage design will be determined by results through Study Part 2 stage 1.

All dose level and enrollment decisions will be formally communicated to investigators via a memorandum.

The dosing schedule is described by a [schema](#) in the protocol synopsis.

6.2.1.3 Dosage Adjustments, Delays, Rules for Withholding or Restarting, Permanent Discontinuation: AMG 820

A subject experiencing a DLT (days 1-21) will not receive additional AMG 820 plus pembrolizumab treatment and will be followed until resolution of the event or toxicity. Subjects withdrawn from AMG 820 plus pembrolizumab therapy will be treated as deemed appropriate by the investigator. End of study procedures should be performed and the appropriate CRFs should be completed. Any treatment related toxicity meeting the DLT definition after day 21 may result in discontinuation of therapy. In subjects with irPR, irCR or evidence of clinical benefit (as determined by the investigator), an option to continue at the same dose level or a lower dose level can be considered. If deemed appropriate by the investigator and sponsor, AMG 820 can be re-initiated once the

toxicity returns to the subject's baseline value or CTCAE grade ≤ 1 . For subjects with hepatotoxicity, refer to [Section 6.4](#). For such subjects, there will be an increased frequency of monitoring at an interval deemed appropriate by the investigator and sponsor. Subjects requiring more than 6 weeks from the last dose to recover from AMG 820 and/or pembrolizumab related grade 3 or 4 toxicities that meet the definition of a DLT will be permanently discontinued (please also see [Table 2](#) for additional details).

If a subject experiences \geq grade 3 toxicities or SAEs that are unrelated to AMG 820 and/or pembrolizumab, then treatment will be postponed until the toxicity has resolved to grade 1 (as defined by the CTCAE, version 4) or returns to the subject's baseline value. If the treatment break is longer than 6 weeks from the last dose the subject may resume treatment only after discussing the case with the Sponsor. If resuming treatment, AMG 820 may be administered at the same dose level or a lower dose level as per the Principal Investigator and Sponsor.

In the event one of the combination drugs is delayed or permanently discontinued for related toxicity, the subjects will have the option to continue on the other drug as long as the toxicity is clearly not related to the combination partner and the investigator and Sponsor assessment is that the patient may derive benefit from continuation with monotherapy.

6.2.2 Non-Amgen Investigational Product: Pembrolizumab

Non-Amgen investigational product pembrolizumab will also be used in this study. Pembrolizumab will be manufactured by Merck. Pembrolizumab will be labeled, packaged, and distributed by Amgen (or designee) using Amgen (or designee) clinical study drug distribution procedures. Pembrolizumab is supplied as pembrolizumab 100 mg/4mL vials (25 mg/mL) solution for intravenous infusion.

Additional details regarding the pembrolizumab product are provided in the IPIM.

6.2.2.1 Dosage, Administration, and Schedule: Pembrolizumab

Pembrolizumab must be prepared and administered by a qualified healthcare professional. Subjects should be assessed clinically for adverse events/toxicity prior to each dose using the CTCAE version 4 ([Appendix A](#)). Complete blood count with differential and chemistry panels including liver enzyme laboratory tests (ALT and AST) and total bilirubin and thyroid function tests (triiodothyronine [T3] or free T3 [FT3] per local standard, free thyroxine [FT4], and thyroid stimulating hormone [TSH]) should be obtained according to the Schedule of Assessments ([Table 5](#)) and the results should be

checked within 2 days prior to each treatment. Dosing will occur only if these test values are acceptable per Section 6.2.2.2.

Pembrolizumab at a dose of 200 mg will be administered intravenously Q3W (\pm 3 days). AMG 820 and pembrolizumab should be administered on the same day, with AMG 820 administered first. The pembrolizumab infusion is to begin 15 minutes following the end of the AMG 820 infusion. Pembrolizumab dosing will continue as long as there is derived clinical benefit, until confirmed PD per irRECIST, intolerance to treatment, 24 months from the date of the first dose of pembrolizumab or end of study, whichever occurs first.

Pembrolizumab infusion will be administered as a 30-minute intravenous infusion. Investigators should make every effort to target infusion timing to be as close to 30 minutes as possible. However, given the variability of infusion pumps from site to site, a window of -5 and +10 minutes is permitted (ie, infusion time is 30 minutes:-5 minutes/+ 10 minutes). A central catheter is not required for infusion; however if a subject has a central venous catheter in place, it is recommended that it be used for the infusion. A 0.2 or 0.22 μ m in-line filter made of polyethersulfone must be used during administration to remove any adventitious particles. If the infusion set does not contain a 0.2 or 0.22 μ m in-line filter, it is recommended to use an extension line containing the filter. Details on the dose calculation, preparation, and administration are provided in the IPIM.

The dose, start date, and lot number of pembrolizumab are to be recorded on each subject's CRF.

6.2.2.2 Dosage Adjustments, Delays, Rules for Withholding or Restarting, Permanent Discontinuation: Pembrolizumab

Pembrolizumab will be withheld for treatment-related adverse events as described in [Table 2](#).

Table 2. Dose Modification Guidelines for Pembrolizumab Related Adverse Events

Toxicity	Hold Pembrolizumab Treatment For Grade	Timing for Restarting Treatment	Treatment Discontinuation
Diarrhea/Colitis	2-3	Toxicity resolves to grade 0-1.	Toxicity does not resolve within 12 weeks of last dose or inability to reduce corticosteroid to 10 mg or less of prednisone or equivalent per day within 12 weeks.
	4	Permanently discontinue	Permanently discontinue
AST, ALT, or Increased Bilirubin ³	2	Toxicity resolves to grade 0-1	Toxicity does not resolve within 12 weeks of last dose.
	3-4	Permanently discontinue (see exception below) ¹	Permanently discontinue
Type 1 diabetes mellitus (if new onset) or Hyperglycemia	Type 1 diabetes mellitus or 3-4	Hold pembrolizumab for new onset Type 1 diabetes mellitus or grade 3-4 hyperglycemia associated with evidence of beta cell failure.	Resume pembrolizumab when subjects are clinically and metabolically stable.
Hypophysitis	2-4	Toxicity resolves to grade 0-1. Therapy with pembrolizumab can be continued while endocrine replacement therapy is instituted	Toxicity does not resolve within 12 weeks of last dose or inability to reduce corticosteroid to 10 mg or less of prednisone or equivalent per day within 12 weeks.
Hyperthyroidism	3	Toxicity resolves to grade 0-1	Toxicity does not resolve within 12 weeks of last dose or inability to reduce corticosteroid to 10 mg or less of prednisone or equivalent per day within 12 weeks.
	4	Permanently discontinue	Permanently discontinue
Hypothyroidism		Therapy with pembrolizumab can be continued while thyroid replacement therapy is instituted	Therapy with pembrolizumab can be continued while thyroid replacement therapy is instituted.
Infusion Reaction	3-4	Permanently discontinue	Permanently discontinue
Pneumonitis	2	Toxicity resolves to grade 0-1	Toxicity does not resolve within 12 weeks of last dose or inability to reduce corticosteroid to 10 mg or less of prednisone or equivalent per day within 12 weeks.
	3-4 or Recurrent 2	Permanently discontinue	Permanently discontinue

Page 1 of 2

Note: Permanently discontinue for any severe or grade 3 drug-related adverse event that recurs or any life-threatening event.

AST = aspartate aminotransferase ALT = alanine aminotransferase

¹ For subjects with liver metastasis who begin treatment with grade 2 AST or ALT, if AST or ALT increases by greater than or equal to 50% relative to baseline and lasts for at least 1 week then subjects should be discontinued.

² Subjects with intolerable or persistent grade 2 drug-related adverse event may hold study medication at physician discretion. Permanently discontinue study drug for persistent grade 2 adverse reactions for which treatment with study drug has been held, that do not recover to grade 0-1 within 12 weeks of the last dose

³ Subjects who have isolated elevated AST (with grade ≤ 1 ALT and normal bilirubin) attributed to AMG 820 and are clinically asymptomatic may potentially continue with treatment upon discussion and agreement with Medical Monitor.

Table 2. Dose Modification Guidelines for Pembrolizumab Related Adverse Events

Toxicity	Hold Pembrolizumab Treatment For Grade	Timing for Restarting Treatment	Treatment Discontinuation
Renal Failure or Nephritis	2	Toxicity resolves to grade 0-1	Toxicity does not resolve within 12 weeks of last dose or inability to reduce corticosteroid to 10 mg or less of prednisone or equivalent per day within 12 weeks.
	3-4	Permanently discontinue	Permanently discontinue
All Other Drug-Related Toxicity ²	3 or Severe	Toxicity resolves to grade 0-1	Toxicity does not resolve within 12 weeks of last dose or inability to reduce corticosteroid to 10 mg or less of prednisone or equivalent per day within 12 weeks.
	4	Permanently discontinue	Permanently discontinue

Page 2 of 2

Note: Permanently discontinue for any severe or grade 3 drug-related adverse event that recurs or any life-threatening event.

AST = aspartate aminotransferase ALT = alanine aminotransferase

¹ For subjects with liver metastasis who begin treatment with grade 2 AST or ALT, if AST or ALT increases by greater than or equal to 50% relative to baseline and lasts for at least 1 week then subjects should be discontinued.

² Subjects with intolerable or persistent grade 2 drug-related adverse event may hold study medication at physician discretion. Permanently discontinue study drug for persistent grade 2 adverse reactions for which treatment with study drug has been held, that do not recover to grade 0-1 within 12 weeks of the last dose.

In case of related toxicity that does not resolve to grade 0 to 1 or baseline within 12 weeks after the last infusion of pembrolizumab, pembrolizumab treatment should be discontinued after consultation with the Sponsor medical monitor. With the investigator and Sponsor medical monitor agreement, subjects with laboratory adverse events still at grade 2 after 12 weeks may continue pembrolizumab treatment in the trial only if asymptomatic and controlled.

Subjects enrolled in phase 1b, who develop a DLT during the DLT evaluation period will permanently discontinue pembrolizumab. In subjects who develop a DLT clearly related to AMG 820 and have evidence of clinical benefit (as determined by the investigator), an option to continue at the same AMG 820 dose level or a lower dose level can be considered. If deemed appropriate by the investigator and sponsor, treatment can be re-initiated once the toxicity returns to the subject's baseline value or CTCAE grade ≤ 1. The reason for dose changes is to be recorded on each subject's CRF.

6.2.3 Management of AMG 820 Related Periorbital or Conjunctival Swelling

If a subject experiences grade 3 (severe) periorbital or conjunctival swelling, the study treatment should be withheld until the toxicity resolves or improves to grade 2 (moderate). If the event requires > 4 weeks to recover to grade 2 or lower (with or

without appropriate therapeutic intervention), the subject will be discontinued from the study and should be followed until the swelling resolves to grade 2. Appropriate therapeutic intervention (eg topical 1% hydrocortisone with 0.25% phenylephrine and/or diuretics) to resolve the swelling may be administered at the discretion of the Investigator to any subject experiencing periorbital edema or conjunctival swelling of any grade.

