2.3 Risk Assessment

There are no important identified risks for AMG 820.

Important potential risks for AMG 820 include increased extracellular matrix, infection, growth plate changes and immunogenicity. Refer to the [AMG 820 IB](#) for additional risk information.

No significant risks or drug-drug interactions with pembrolizumab are anticipated at the AMG 820 starting dose of 1400 mg in the proposed study. Explored AMG 820 dose levels ranging from 0.5 mg/kg QW and 1.5mg/kg to 20 mg/kg Q2W were generally well-tolerated in the FIH study. Approximately 25 subjects have received AMG 820. Treatment-related toxicities have been mild or moderate in most patients, and the most common toxicities are transient aspartate aminotransferase increase and periorbital edema. No subjects have developed treatment emergent neutralizing antibodies.

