6.2.1.2.3 Dose-limiting Toxicity Definition

An adverse event will be considered related to study treatment (possibly, probably, or definitely related to the study treatment) if there is a suspected “reasonable causal relationship” to the study treatment (ICH E2A), and not only a lack of an alternative explanation for the toxicity. All toxicities will be graded using the CTCAE version 4.0 ([Appendix A](#)).

The occurrence of any of the following toxicities during DLT evaluation period (ie, 21 day period from the initial administration of AMG 820 and pembrolizumab in combination) will be considered a DLT, if judged by the investigator to be related to the administration of AMG 820 and/or pembrolizumab:

- Grade 4 non-hematologic toxicity
- Grade 3 or higher pneumonitis
- Grade 3 non-hematologic toxicity lasting > 7 days despite appropriate treatment
 - Grade 3 fatigue will not be classified as DLT, irrespective of duration
- Any grade 3 or higher non-hematologic laboratory value if:
 - medical intervention is required, or
 - the abnormality leads to hospitalization, or
 - the abnormality persists at grade 3 or higher for >1 week unless deemed not clinically important per both investigator and sponsor
- Grade 3 or grade 4 febrile neutropenia

- Grade 3 or higher thrombocytopenia with bleeding and Grade 4 or higher thrombocytopenia lasting > 48 hours or any thrombocytopenia requiring intervention
- Delay in cycle 2 treatment for > 2 weeks due to study drug-related toxicity (unless clearly attributable to pembrolizumab only and delay is caused due to tapering of steroids)
- Any other intolerable toxicity leading to permanent discontinuation of AMG 820 or pembrolizumab

Lymphopenia of any grade is not considered a DLT

Dose limiting toxicities do not include the following:

- A transient (resolving to grade ≤ 1 within 6 hours of onset) grade 3 infusion-related adverse event
- Any grade 3 endocrinopathy that is adequately controlled by hormonal replacement

Cumulative adverse events profile will be taken into consideration when making decisions on dose escalation or de-escalation.

If an AE is clearly attributable to pembrolizumab (based on its known safety profile) and does not exceed the expected severity, this specific AE may be considered exempt from being a DLT.

Disease related events should not be considered a DLT.

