Any subject meeting the criteria for Hy's Law case (ie, severe drug-induced liver injury) will be considered a DLT. A Hy's Law case is defined as: AST or ALT values of $\geq 3 \times$ ULN AND with serum total bilirubin level (TBL) of $> 2 \times$ ULN without signs of cholestasis and with no other clear alternative reason to explain the observed liver-related laboratory abnormalities (see [Section 6.4](#) on hepatotoxicity management and [Appendix A](#) for further explanation of Hy's law case and Management of Hepatic Function).

If a subject experiences a DLT during the DLT evaluation period, study treatment should be discontinued for that subject. Additionally, any treatment related toxicity meeting the DLT definition after day 21 should result in discontinuation of therapy. In subjects with irPR, irCR or evidence of clinical benefit (as determined by the investigator), an option to continue at the same or at a reduced dose level can be considered once the toxicity returns to the subject's baseline value or CTCAE grade ≤ 1 if deemed appropriate by the investigator and sponsor.

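### For AMG 820-related grade 3 periorbital or conjunctival swelling that lasts more than 7 days despite treatment, Section 6.2.3 and the DLT rules give opposite instructions on stopping and restarting

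*Protocol*

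**What the plan says.** Protocol Section 6.2.3 covers swelling related to AMG 820. At grade 3, "the study treatment should be withheld until the toxicity resolves or improves to grade 2 (moderate". Its only stopping provision is a time limit: "If the event requires > 4 weeks to recover to grade 2 or lower", with or without intervention, the subject is discontinued. The section does not mention DLTs and does not claim precedence over other rules.

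Section 6.2.1.2.3 counts as a DLT, if related and occurring in the 21-day window, "Grade 3 non-hematologic toxicity lasting > 7 days despite appropriate treatment". The one exception attached to that item is "Grade 3 fatigue will not be classified as DLT, irrespective of duration". The section's other exemptions are lymphopenia, brief grade 3 infusion reactions, hormonally controlled endocrinopathy, events clearly due to pembrolizumab, and disease-related events. Swelling is not among them.

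On consequences, the same section says "If a subject experiences a DLT during the DLT evaluation period, study treatment should be discontinued for that subject", and that after the window "any treatment related toxicity meeting the DLT definition after day 21 should result in discontinuation of therapy". It allows continuation for subjects with irPR, irCR or clinical benefit, once the toxicity is back to baseline or "CTCAE grade ≤ 1 if deemed appropriate by the investigator and sponsor".

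Section 6.2.1.3 gives no further combination treatment after a DLT in days 1-21. For later events that meet the DLT definition it uses *may* where 6.2.1.2.3 uses *should*. It repeats the baseline or grade 1 threshold, and it requires permanent discontinuation if recovery from a related grade 3 or 4 DLT-type toxicity takes more than 6 weeks from the last dose. Section 6.2.2.2 permanently discontinues pembrolizumab after a DLT in the Phase 1b window. It then offers continuation where the DLT is clearly related to AMG 820 and there is clinical benefit, again at baseline or grade 1 or lower.

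**The concern.** Swelling around the eye is an expected effect of this drug. Section 2.3 reports that "the most common toxicities are transient aspartate aminotransferase increase and periorbital edema". That is presumably why the protocol gives it a section of its own, and a site faced with a grade 3 case will look there first. Section 6.2.3 tells the site to hold and then resume. The DLT text tells the same site that the subject has had a dose-limiting toxicity and is to stop. Both instructions are in the current protocol, and neither section points to the other.

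What is at stake is who stays on treatment. In Part 1, a subject who meets the DLT definition could be re-dosed by a site following 6.2.3. In Part 2, two sites could treat the same event in opposite ways and both cite the protocol.

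**Working it through.** No sample size, power or error rate enters this point, and the plan states no figure to reproduce. The check follows one AMG 820-related, treated grade 3 swelling through each rule, according to how long it stays at grade 3.

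| Time at grade 3 | Section 6.2.3 | DLT and restart rules (6.2.1.2.3, 6.2.1.3, 6.2.2.2) | Result |
|---|---|---|---|
| 7 days or less | Resume at grade 2 | The more-than-7-days criterion is not met | No conflict from this criterion |
| More than 7 days, up to 4 weeks, in days 1-21 | Resume at grade 2 | DLT; treatment stops; restart only with response or clinical benefit, at baseline or grade 1 or lower | Conflict on stopping and on restart grade |
| More than 7 days, up to 4 weeks, after day 21 | Resume at grade 2 | *Should* stop (6.2.1.2.3) or *may* stop (6.2.1.3); restart as above | Conflict on restart grade; the stop rule depends on the section read |
| More than 4 weeks | Discontinue | Permanent discontinuation when recovery takes more than 6 weeks from last dose | Time limits differ |

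**A worked case.** Dose on day 1. Swelling reaches grade 3 on day 5, stays there for 10 days despite treatment (days 5 to 14), and is grade 2 from day 15.
- Duration: 10 days is more than 7 and less than 28, so the event is a DLT under 6.2.1.2.3 and within the 4-week limit of 6.2.3.
- Under 6.2.3 the hold ends on day 15, and the next dose, due on day 22, may be given at grade 2.
- Under 6.2.1.2.3 and 6.2.1.3 the day-22 dose is not given. Even if the clinical-benefit option is used, grade 2 does not meet a threshold of baseline or grade 1, assuming that the subject had no such swelling at baseline.

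**The two time limits.** Counting the 4 weeks from onset, which 6.2.3 does not specify, the limit for this event is day 5 + 28 = day 33. Six weeks from the last dose is day 1 + 42 = day 43. The limits are 10 days apart. They coincide only if onset is 42 - 28 = 14 days after the last dose, and with later onset their order reverses.

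**Table 2.** Its row for all other drug-related toxicity requires grade 0-1 before restart. The table is titled for pembrolizumab-related events, so it adds a conflict only if the swelling is also attributed to pembrolizumab.

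**Which DLT definition was used.** SAP Section 6 summarises a DLT as any related grade 3 or higher event in the window and refers to the protocol for details. The check uses the protocol definition.

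**The case against.** The best defence is that a specific rule overrides a general one. Section 6.2.3 is written for this toxicity, and the DLT text is written for all toxicities. That is a reasonable reading, but the protocol never states it. Elsewhere it writes its exceptions out. The DLT section names its exemptions, 6.2.1.3 sends hepatotoxicity to Section 6.4, and isolated AST elevation attributed to AMG 820 has its own allowance in Table 2 (footnote 3) and in 6.2.4.6. Swelling, the other most common AMG 820 toxicity, has no matching sentence in the DLT or restart rules.

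Other objections limit the point, and they stand:
- A reader might infer that the conflict covers every event that settles at grade 2. It does not. The grade 1 threshold in 6.2.1.2.3 and 6.2.1.3 for related toxicity is tied to events meeting the DLT definition, and a grade 3 event of 7 days or less does not meet the duration criterion.
- A reader might infer that it covers every grade 3 event of 8 to 28 days. The DLT criterion requires relatedness and persistence despite appropriate treatment, whereas 6.2.3 leaves intervention to the investigator's discretion. An untreated event is not clearly a DLT under that criterion.
- After day 21, *may* in 6.2.1.3 leaves room for a hold-and-resume rule. The firm clash over stopping is therefore in days 1-21.
- Section 6.2.3 is silent on DLT classification, so it does not alter how DLTs are counted or the 6+3 decision. Some doubt about re-dosing after a DLT also exists without it, because of the clinical-benefit options.

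**Conclusion.** The contradiction holds for AMG 820-related grade 3 periorbital or conjunctival swelling that persists more than 7 days despite appropriate treatment. In days 1-21 the sections disagree on whether treatment stops and on the restart grade. After day 21 they still disagree on the restart grade (2 against 1 or lower, or baseline), and the stop rule differs between 6.2.1.2.3 and 6.2.1.3. The recovery limits also differ: 4 weeks against 6 weeks from the last dose.

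How often this would arise cannot be said. A reader might infer from the word common that such events are frequent, and attach a probability per Part 1 cohort. The documents do not support that. They give no rate of grade 3 swelling. Section 2.2.1 describes periorbital edema without clinical sequelae among 25 subjects, and the one DLT that it names is bilateral deafness. Section 2.3 calls treatment-related toxicities mild or moderate in most patients.

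This is a textual inconsistency with a safety consequence for individual subjects, and it should be corrected. It does not invalidate the DLT endpoint. The Amendment 2 rationale says that the sponsor has decided to stop investigating the combination, which limits future impact. Section 3.5.1 allows treatment for up to 24 months, so the rules still bind anyone on treatment.

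**What to change.** Reconcile Sections 6.2.3, 6.2.1.2.3, 6.2.1.3 and 6.2.2.2, and Table 2 where the event is also attributed to pembrolizumab. The text should state:
- which section governs AMG 820-related grade 3 swelling;
- whether such an event lasting more than 7 days despite treatment counts as a DLT;
- whether a subject with such an event may be re-dosed and, if so, the recovery grade that applies;
- which time limit applies and the date from which it runs;
- whether a DLT-type toxicity after day 21 *should* or *may* end therapy, in the same words in both sections.

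The choice of clinical rule belongs to the sponsor; the protocol needs to give one. The DLT summary in SAP Section 6 should then be checked against the result. The cost is an exception or precedence sentence with cross-references in an amendment, and no added visits or procedures.
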